2.0 Specific Aims

2.1 Specific Aim #1 (primary aim):

- To determine the effect of Doxycycline vs. placebo on the need for additional treatment for unacceptable bleeding at 13 weeks post-randomized treatment.

2.2 Specific Aim #2 (secondary aim):

- To determine if initial treatment with Doxycycline results in higher patient satisfaction with ESI as compared to placebo at 13 weeks post-randomized treatment.

2.3 Specific Aim #3 (secondary aim):

- To determine method continuation and patient satisfaction rate at 26 week post-randomization in patients who choose secondary treatment with Doxycycline for unacceptable bleeding at 13 weeks post-randomized treatment.

In order to evaluate specific aim #1:

- All ESI patients will be offered enrollment in the study at ESI insertion and will begin prospective diaries. They will be contacted at 13 weeks post insertion. If patients report unacceptable bleeding at that time or self-report at any time following an initial 13 week interval, they will be offered randomization to Doxycycline or placebo. Patients will continue a weekly prospective symptom diary for the duration of study.
- Time to recurrence of unacceptable bleeding post-treatment and need for secondary treatment (primary endpoint) will be determined by completion of prospective symptom recording by 13 weeks post-randomized treatment.

- Side-effects and adverse events associated with medical treatment will be documented.

In order to evaluate specific aim #2:

- A patient satisfaction survey will be administered at randomization and 13 weeks post-randomization. The results will be compared between the Doxycycline and placebo study arms.

In order to evaluate specific aim #3:

- Patient satisfaction will be assessed at 13 weeks post-ESI insertion.
- Patients who report unacceptable bleeding after initial randomized treatment and who choose additional treatment will receive secondary treatment with Doxycycline and the method continuation rate and patient satisfaction rate at 26 weeks post randomization will be calculated.
- In patients who leave the study prior to 26 weeks post-randomization, patient satisfaction will be recorded at that time.
- If ESI is removed prior to 26 weeks post-enrollment, the reason, date of removal and alternative contraception will be documented.

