5.2.1 Patient selection

After appropriate IRB approval, ESI users aged 18-51 years old who meet the inclusion and exclusion criteria, and sign a written consent will be **enrolled in the study at the time of ESI insertion**. Every effort will be made to insert ESI on the same day as consent unless medically contraindicated. They will complete a prospective symptom diary from date of ESI insertion. All patients will be contacted by study personnel 13 weeks after enrollment and queried as to the presence of unacceptable bleeding. Bleeding concerns will be objectively assessed using a modification of the Pictorial Blood Loss Assessment Chart (PBLAC) [27]. Patient-initiated contact in with bleeding concerns at any time after 13 weeks post ESI insertion will result in enrollment and randomization at the time of contact. **The basis for randomized treatment will be whether or not the bleeding is “unacceptable” to the patient. This is inherently subjective, but constitutes the basis for most removal requests.** Patients who report unacceptable bleeding at 13 weeks post-ESI insertion, and those who call with bleeding concerns after 13 weeks post ESI insertion, will be randomized into two groups (Doxycycline or placebo). Patients who do not report unacceptable bleeding will continue to complete diaries and may be eligible for randomized treatment if unacceptable bleeding develops. Patients will receive diaries sufficient for completion of the study with instructions to contact study personnel if more diaries are needed or if diaries are lost. Patients and investigators will be blinded to the group assignment as well as the study coordinator who will be responsible dispensing of appropriate study medication by the pharmacy.

Patients who continue to have unacceptable bleeding after 4 weeks post-randomized treatment and wish to have secondary treatment will be treated with Doxycycline. Secondary treatment will not be blinded. Rates of unacceptable bleeding and patient satisfaction scores at 26 weeks post-randomized treatment in remaining study participants will be calculated.

[figure not shown]

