If a patient reports bleeding concerns as described in section 5.2.1 and is randomized to the placebo group, she will be given a pill bottle containing placebo made to look identical to treatment to be taken twice daily for 10 days. Patient and investigators will be blinded as to group assignment.

d. Doxycycline group

If patient has bleeding concerns determined in section 5.2.1 and is randomized to the Doxycycline group, she will be given a pill bottle containing Doxycycline 100 mg to be taken twice daily for 10 days. Patient and investigators will be blinded as to group assignment. Patients who experience unacceptable bleeding but are not bleeding at the time of study personnel contact will be instructed to call back if unacceptable bleeding recurs for randomization to treatment or placebo.

e. Treatment compliance process

Pill counts at the end of each treatment course will be performed to assess patient compliance with treatment. A pill diary given to patients at the time of randomization will provide temporal correlation between treatment initiation and bleeding symptoms.

f. Symptom recording

Upon enrollment and ESI insertion, patients will begin a weekly prospective symptom diary in order to self-assess bleeding and additional symptoms for a **total of 39 weeks from study enrollment**. A modification of the PBLAC where 1= no bleeding, 2=spotting requiring 1-2 panty-liners per 24 hours only, 3= bleeding requiring 1-3 tampons/pads in 24 hours, 4=bleeding requiring 4-6 tampons/pads per 24 hours, and 5=bleeding requiring >6 tampons/pads per 24 hours will be utilized for bleeding recording.[27] Bleeding diaries will be collected every 13 weeks and completion will be required for continued enrollment in the study and receipt of remuneration after every 13 week interval. Patients will also record any other associated symptoms such as headache, mood changes, acne and intolerance to treatment detailed in sections 6.2.2 and 6.2.3. Prospective symptom diary can be captured on a paper formate or via Mayo Clinic website RED Cap.

A bleeding episode is defined by the WHO as any set of one or more bleeding days (either consecutive or separated by only one bleeding-free day) bounded at each end by two or more bleeding-free days. **The bleeding pattern will be analyzed within each 13-week reference period** and categorized into 6 groups [4, 13, 14]:

- Amenorrhea (no bleeding during the reference period),
- Infrequent bleeding (fewer than 3 bleeding episodes),

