- Normal bleeding frequency (3-5 bleeding episodes).
- Frequent bleeding (more than 5 bleeding episodes),
- Prolonged bleeding (1 or more bleeding episodes lasting 14 days or more)

Subgroup analysis may provide additional insight into the efficacy of treatment for various bleeding patterns.

g. Patient satisfaction surveys

Patients will be asked to fill out short satisfaction surveys at randomization measuring satisfaction prior to any treatment, and at 13 and 26 weeks post randomization (see appendix). If patient has their ESI removed prior to 26 weeks post randomization, she will be given a final satisfaction survey at removal. Patient satisfaction surveys will be recorded on a paper formate or via Mayo Clinic website RED Cap.

Patients will rate their satisfaction with a) ESI and b) bleeding with ESI on a 5-point Likert scale ranging from very satisfied to very dissatisfied. If patient has ESI removed prior to 26 weeks post-study enrollment, she will be given a final satisfaction survey at removal.

h. Treatment issues

At enrollment, patients will be provided with a contact number allowing them to reach study personnel at all times with concerns. Instructions will be provided for instances of drug intolerance/allergy, heavy bleeding or other ESI related issues and clinical appointments for evaluation scheduled as needed.

i. Secondary Treatment

If a patient reports unacceptable bleeding at >4 weeks post randomization to treatment or placebo, study participation will be recorded as **need for additional treatment, and will represent the primary endpoint**. If she wishes to have secondary treatment, she will be treated with Doxycycline. Treatment will be limited to two interventions per 13 week

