Patients will be analyzed according to their randomized treatment arm. All calculated p-values will be two-sided and p-values less than 0.05 will be considered statistically significant. Analyses will be performed using SAS software package (version 9.2). Comparisons of categorical endpoints (e.g. need for additional treatment, bleeding pattern based on the WHO classification, presence of adverse event(s), satisfaction survey questions) between the two arms will be evaluated using the chi-square test. Additional comparisons of these endpoints, adjusted for potential confounders, will be assessed by fitting separate logistic regression models. Time-to-event methodology (e.g. Kaplan-Meier method and Cox proportional hazards regression models) will be utilized for binary versions of these endpoints if patient follow-up becomes an issue and patients don't comply with the planned follow-up before completing the study. Poisson regression models will be used to compare the diary responses between the treatment arms. In the Poisson model, the endpoint will be the number of bleeding and spotting days per patient (and likewise the number of days with additional symptoms), offset by the total days of diary follow-up per patient. Ninety-five percent confidence intervals (95% CI) will be constructed around the estimates for method continuation and satisfaction.

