7.1 Study Duration

Patients will be offered enrollment in the study upon ESI insertion. They will begin completing weekly prospective symptom diaries at that time. If they report unacceptable bleeding at the time of study personnel contact at 13 weeks post ESI insertion or self-report unacceptable bleeding at > 13 weeks post ESI insertion, they will be offered randomization to Doxycycline or placebo. They will continue prospective weekly symptom diaries for 26 weeks post randomization or until they discontinue study participation. A patient who self-reports unacceptable bleeding late in the study interval will be followed for at least 13 weeks after randomized treatment in order to have a meaningful study conclusion. The maximum study length for such a patient would be 52 weeks from ESI insertion. Based on current numbers of ESI insertions per year, **we anticipated that all 100 subjects with unacceptable bleeding will randomized within 30 months. However, the rate of reported unacceptable bleeding was lower than expected and therefore we propose an additional enrollment of 120 patients (total 470 patients) to achieve 100 randomized patients.**

8.0 Study Expectations and Limitations:

This study is a double blinded placebo-controlled randomized prospective trial of Doxycycline for the management of ESI-related unacceptable bleeding. The study will include US women regardless of BMI. Randomization will be done using a dynamic

allocation process with stratification by age, BMI and postpartum status. This will avoid confounding effects of these variables on our outcomes.

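### Adverse events and symptom days are compared by randomized arm with no cut-off at open-label doxycycline; at the plan's own rates, any overlap would on net dilute the safety comparison

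*Combined protocol and SAP*

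**What the plan says.** Section 5.4.2 sets the rule for all comparisons: "Patients will be analyzed according to their randomized treatment arm". For adverse events, "presence of adverse event(s), satisfaction survey questions) between the two arms will be evaluated using the chi-square test", with adjusted logistic models as a supplement. For diary data, a Poisson model counts bleeding and spotting days ("and likewise the number of days with additional symptoms), offset by the total days of diary follow-up per patient"). No censoring rule or on-treatment window is given for either.

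Open-label treatment is described in section 5.2.1: "Patients who continue to have unacceptable bleeding after 4 weeks post-randomized treatment and wish to have secondary treatment will be treated with Doxycycline". It is unblinded and available to both arms. Section 5.3.1.i adds a cap: "Treatment will be limited to two interventions per 13 week" interval. Aim 3 in section 2.3 points to a later start, since it concerns continuation and satisfaction "in patients who choose secondary treatment with Doxycycline for unacceptable bleeding at 13 weeks post-randomized treatment".

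On follow-up, section 7.1 says: "They will continue prospective weekly symptom diaries for 26 weeks post randomization or until they discontinue study participation". Among other symptoms, the diary records "acne and intolerance to treatment detailed in sections 6.2.2 and 6.2.3" (section 5.3.1.f); section 6.2.3 is the list of doxycycline reactions. Section 5.3.2.B names a symptom comparison at 13 weeks after randomization. Its adverse-event item has no time window.

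Sections 5.3.2.E and F are both headed as efficacy and safety endpoints for secondary treatment. They list continuation, removals with reasons, and replacement contraception, but no adverse events.

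**The concern.** A placebo-arm woman who takes open-label doxycycline and reacts to it is counted, under 5.4.2, as a placebo-arm event. The randomized comparison is the only one that can separate reactions to a 10-day course from background symptoms. If many placebo women have taken the drug before counting stops, a similar event rate in the two arms could be read as reassurance when it partly reflects shared exposure.

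The women who take open-label doxycycline could also outnumber those randomized to it: 62 from the arm rates, or 66 as stated in 5.4.1, against 50. No adverse-event rate is planned for them.

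**Working it through.** **Inputs from the plan (5.4.1).** 50 women per arm; 44% (doxycycline) and 80% (placebo) expected to need additional treatment; two-sided alpha 0.05. These inputs reproduce the stated power for the primary endpoint: a two-proportion normal approximation gives 97.0%, consistent with the stated figure of more than 90%. The arm rates give 22 + 40 = 62 women needing additional treatment; the plan says 66.

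**Inputs the plan does not give (assumed).**
- g: the share of women needing additional treatment who take one open-label course inside the window. It combines uptake and timing.
- p0 and pd: the probability of an event per treatment window on placebo and on doxycycline.
- Two independent windows, blinded and later. The extra risk per course is r = 1 − (1 − pd)/(1 − p0).

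**Count of courses.** Placebo arm 40g; doxycycline arm 50 + 22g; difference 50 − 18g. This is 50, 41 and 32 at g = 0, 0.5 and 1. If each course adds the same symptom days, the expected excess falls by 0%, 18% and 36%. If repeat courses add nothing, the difference is 50 − 40g, and the excess falls by 0%, 40% and 80%.

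**Presence of an event.**
- Placebo: 1 − (1 − p0)²(1 − 0.80·g·r)
- Doxycycline: 1 − (1 − p0)²(1 − r)(1 − 0.44·g·r)
- The ratio of the diluted to the undiluted risk difference simplifies to 1 − g[0.80 − 0.44(1 − r)].

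| Assumed p0 vs pd | g = 0 | g = 0.5 | g = 1 | Shrinkage at g = 0.5, 1 |
|---|---|---|---|---|
| 5% vs 10% | 9.75 vs 14.50; diff 4.75 | 11.65 vs 15.49; diff 3.84 | 13.55 vs 16.48; diff 2.93 | 19%, 38% |
| 10% vs 20% | 19.0 vs 28.0; diff 9.0 | 22.6 vs 29.8; diff 7.2 | 26.2 vs 31.5; diff 5.3 | 20%, 41% |
| 10% vs 30% | 19.0 vs 37.0; diff 18.0 | 26.2 vs 40.1; diff 13.9 | 33.4 vs 43.2; diff 9.8 | 23%, 46% |

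(Percent, placebo vs doxycycline; differences in points.)

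**Direction.** With placebo uptake qP and doxycycline-arm uptake qD, the ratio is 1 − qP + qD(1 − r). It is below 1 unless qP < qD(1 − r). At qP = 0.80 and qD = 0.44 the net effect is dilution. With equal uptake of 0.60 and r = 0.20 it is 1 − 0.60 + 0.48 = 0.88, still dilution. With uptake only in the doxycycline arm it is 1 + 0.44(1 − r), or 134 to 142% of the true difference across the three scenarios, so the gap widens.

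**Power** (normal approximation, pooled variance, 50 per arm, in the expected direction) at g = 0, 0.5, 1: 0.108, 0.081, 0.060 for 5% vs 10%; 0.183, 0.125, 0.085 for 10% vs 20%; 0.518, 0.312, 0.168 for 10% vs 30%. A single 4-week window gives 0.155, 0.286 and 0.711 for the three scenarios. Part of that gain comes from the shorter window, which carries less background noise.

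**The case against.** *Comparison by randomized arm is legitimate.* It is; it answers a treatment-policy question and should stay. It does not show whether one course causes more reactions than placebo once placebo women have taken the same drug.

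*Secondary treatment may start after week 13.* Aim 3 and the 13-to-26-week removal items in 5.3.2.F support this. On that reading, an analysis stopped at 13 weeks has no bias. But 5.2.1 and 5.3.1.i allow treatment from week 4, and the adverse-event item has no stop.

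*The Poisson model must include the secondary phase.* A reader might infer this from the offset and the 26-week diaries. The documents do not settle it: an offset adjusts for exposure and does not define a window, diaries begin at implant insertion, and 5.3.2.B names a 13-week symptom comparison. What stands is that no cut-off is stated.

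*The list B heading limits the adverse-event item to primary treatment.* If so, the dilution weakens, but secondary treatment then has no adverse-event item. If the item covers all medical treatment, the dilution applies. One half stands on either reading.

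*The named events are mostly not doxycycline reactions.* List B names headache, mood changes, acne and BMI change, and only headache appears in 6.2.3. The other reactions enter through the diary's intolerance entry, so their inclusion in the comparison is an inference.

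*High overlap is doubtful, and the bias is small beside the noise.* The 44%, and the 92% behind the 80%, were removal requests in the earlier cohort, and removal ends participation. Aim 2 in 5.4.1 nevertheless assumes that all who request treatment receive it. At g = 0.5 the loss is about 1 to 2 points in the first two scenarios, against CI half-widths of 10 and 14 points in a 4-week window. This holds and lowers the severity.

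**Conclusion.** The concern holds as a minor point. As written, the comparison has no cut-off at open-label doxycycline, and at the plan's own expected rates the net effect of courses inside the window is dilution. That direction rests on 80% vs 44%, on actual uptake following those rates, and on open-label courses falling inside the window. The 19 to 23% and 38 to 46% losses rest on assumed reaction rates and overlap and should not be read as predictions.

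A reader might infer that every open-label course biases toward no difference. That is not so: courses in the doxycycline arm act the other way, and it is the excess of placebo-arm courses that dilutes. Nor do the documents support saying that safety data go uncollected. Section 6.3 puts all adverse events on case report forms; the gap is in comparison and tabulation. The primary efficacy endpoint is unaffected. Section 8.4 expects few adverse events, so estimates with intervals matter more than the test. This is a cheap improvement.

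**What to change.** In 5.4.2:
- Keep the 13-week comparison as randomized, and state that it may include open-label exposure.
- Add a comparison of adverse events with onset in the first 4 weeks after randomization, before any open-label dose, as a risk difference with 95% CI. From 1.96·√(p0(1 − p0)/50 + pd(1 − pd)/50), the half-width is about 10 points at 5% vs 10% and 14 at 10% vs 20%.
- Add a Poisson analysis of symptom days from the first 4 weekly diary entries, reported as an estimate with 95% CI.
- Do not apply this window to BMI change, which is measured only at enrollment and 26 weeks.

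In 5.3.2.F, add a descriptive table with exact 95% CIs of adverse events after open-label doxycycline, split by original arm: a first course for placebo women, a repeat course for doxycycline women. With no reactors, the upper limit is 1 − 0.025^(1/n): 5.8% for 62 women and 11.2% for 31; for placebo-arm women alone, 8.8% for 40 and 16.8% for 20.

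Cost: analysis wording, one table, and at most one date field for the open-label start if the case report form lacks it. Downside: a shorter window with fewer events.

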3.0 Study Hypotheses

3.1 Study hypotheses for specific aim #1 (primary aim):

- Doxycycline is more effective than placebo in the initial management of ESI-related bleeding.
- **Statistically significant difference between the placebo and Doxycycline groups will be shown in favor of Doxycycline**

3.2 Study hypotheses for specific Aim #2 (secondary aim):

- Patients in the Doxycycline group will report a higher satisfaction rate with ESI scores on a survey as compared to those in the placebo arm at 13 weeks post-randomization.
- **Statistically significant difference in patient satisfaction rates between the placebo and Doxycycline groups will be shown in favor of Doxycycline.**

3.3 Study hypotheses for specific aim #3 (secondary aim):

- In patients who request secondary treatment for unacceptable bleeding, administration of Doxycycline will result in a high method continuation rate and patient satisfaction rate at 39 weeks post ESI insertion.
- The above will be supported by method continuation rate of >75% [3, 8] at 26 weeks post-randomization.

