5.3.2 Outcome measurements

A. Primary treatment efficacy and safety end point (primary endpoint addressing specific aim #1)

- The efficacy of Doxycycline on ESI-related bleeding will be compared to placebo based on rates of **unacceptable bleeding** and weekly prospective symptom diary at 13 weeks post-randomization.

B. Primary treatment efficacy and safety endpoints (secondary endpoints addressing specific aim #1)

- Method continuation rate at 13 weeks post-randomization will be compared for women in the Doxycycline vs. placebo group.
- Bleeding patterns will be quantified based on the PBLAC and WHO classification of clinically important bleeding patterns over each 13 week reference period.[13,14, 29].
- Incidence of additional symptoms including acne, headache, mood changes in the treatment groups will be compared to placebo at randomization and 13 weeks post-randomization based on the weekly prospective symptom diary
- Interval to recurrence of unacceptable bleeding post-randomized treatment (i.e., need for additional treatment) will be determined
- Rate of adverse events associated with medical treatment will be documented by prospective symptom diary and BMI calculation. These include headache, mood changes, acne and change in BMI.

C. Patient satisfaction with primary treatment endpoint (primary endpoint addressing specific aim #2)

- Patient satisfaction with ESI at randomization for a baseline pre-treatment satisfaction and at 13 weeks post-randomized treatment following primary treatment with Doxycycline vs. placebo will be compared

D. Patient satisfaction with secondary treatment endpoint (primary endpoint addressing specific aim #2)

- Patient satisfaction with ESI at 26 weeks post-randomized treatment for patients with continued unacceptable bleeding following primary treatment who receive secondary treatment with Doxycycline will be calculated.

E. Secondary treatment efficacy and safety endpoint (primary endpoint addressing specific aim #3)

- Method continuation rate at 26 weeks post-randomized treatment for patients with continued unacceptable bleeding after primary treatment who undergo secondary treatment with Doxycycline will be calculated

F. Secondary treatment efficacy and safety endpoint (secondary endpoints addressing specific aim #3)

- Rate of ESI removal for bleeding between 13 and 26 weeks post randomization.

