5.4.1 Power statements

Based on prior Mayo data, we anticipate about 30% of patients will develop unacceptable bleeding following ESI insertion.[3,29] These patients will be approached for participation in this study. The study plans to randomize a total of 100 patients with unacceptable bleeding to either placebo (N=50) or Doxycycline (N=50). The following calculations were based on a two-sided chi-square test with a type I error rate of 0.05.

Aim 1: Of the patients with bleeding concerns, based on our prior experience we anticipate that 44% of the patients randomized to Doxycycline will request additional treatment, and about 80% in the placebo arm. We are purposely overestimating the placebo effect over that noted in our cohort (92% removal requests) to allow for variation in the study group. Given the sample size of 50 per treatment arm, the study will have >90% power to detect the anticipated difference in the need for additional treatment.

Aim 2: Across the two arms, we anticipate that 66 of the 100 patients will request additional treatment and will receive additional treatment with Doxycycline. Within this subset we plan to estimate the method continuation rate following additional treatment. Based on a sample size of 66, the ½ width for a 95% CI around an estimate of 75% is ±10%.

Aim 4: Among the anticipated 66 patients who will request additional treatment for continued unacceptable bleeding at 26 weeks post-ESI insertion, we plan to quantify the patient satisfaction rate. If we assume 75% will be “very satisfied” or “satisfied”, then the ½ width for a 95% CI around this estimate will be ±10%.

5.4.2 Proposed Statistical Analysis:

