8.4 Impact of Expected results

The expectation of the study is that we will satisfy our hypotheses and find that

- **The failure of treatment, assessed as the requiring additional treatment, in the Doxycycline group will be statistically significantly lower than in the placebo group (primary endpoint)**
- The rate of removal for bleeding at 13 and 26 weeks post-randomized treatment will be lower in the Doxycycline group as compared to the placebo group though it may not be statistically significantly lower given the expected removal rate [3] and study sample size.
- **The rate of patient satisfaction at 13 and 26 weeks post-randomized treatment will be statistically significantly higher in the Doxycycline as compared to the placebo group**
- The incidence of associated symptoms, adverse events and treatment associated events will be low and consistent with prior studies
- No ESI-related contraceptive failures will be reported regardless of patient BMI.

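### The main week-13 satisfaction test (Aim 2) is an unadjusted chi-square that, read literally, ignores the order of the 5-point item and omits the baseline score and minimization factors: valid, but it gives up power

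*Combined protocol and SAP*

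**What the plan says.** - **Hypothesis.** Section 3.2 expects that women on Doxycycline "will report a higher satisfaction rate with ESI scores on a survey" at 13 weeks, and that a "Statistically significant difference in patient satisfaction rates between the placebo and Doxycycline groups will be shown in favor of Doxycycline". Section 8.4 repeats this: the "rate of patient satisfaction at 13 and 26 weeks post-randomized treatment will be statistically significantly higher in the Doxycycline" group than on placebo.
- **Measurement.** Section 5.3.1(g): "Patients will rate their satisfaction with a) ESI and b) bleeding with ESI on a 5-point Likert scale". The survey is completed at randomization and at 13 and 26 weeks. A woman whose implant is removed early has a further survey: "she will be given a final satisfaction survey at removal".
- **Outcome.** Section 5.3.2(C) lists "Patient satisfaction with ESI at randomization for a baseline pre-treatment satisfaction and at 13 weeks post-randomized treatment" as what is to be compared between arms.
- **Main test.** Section 5.4.2 puts satisfaction among the categorical endpoints: "satisfaction survey questions) between the two arms will be evaluated using the chi-square test". Further logistic models adjusted for potential confounders are planned as additional analyses. Their covariates are not listed, and they are not said to be binary or ordinal.
- **Allocation.** Section 5.3.1(b) minimizes on age (under 30, 30 or over), postpartum status and BMI (under 30, 30 or over).
- **Cut.** The only one is in section 5.4.1, which counts the two most favourable categories together. It applies to women given secondary treatment, of whom the plan says "we plan to quantify the patient satisfaction rate". No cut is stated for the week-13 comparison.

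**The concern.** Three pieces of information are already collected but do not enter the main test: the order of the five categories, the same item's score before treatment, and the factors used to balance the arms. A chi-square on five categories spends 4 degrees of freedom looking for any difference in shape, whereas the hypothesis is directional. Section 5.4.2 later mentions binary versions of these endpoints for time-to-event methods, which suggests that the chi-square would otherwise keep all the categories. The word rates in sections 3.2 and 8.4 points instead to a dichotomy. The plan does not settle which is meant.

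At stake is power on a secondary aim for which the plan predicts statistical significance but gives no between-arm power. The paragraph headed Aim 2 in section 5.4.1 concerns continuation after additional treatment.

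**Working it through.** **Inputs from the documents.** 50 per arm, two-sided 0.05, and 44% versus 80% needing additional treatment (5.4.1); a 5-point item with a score at randomization (5.3.1(g), 5.3.2(C)); three minimization factors (5.3.1(b)). All satisfaction distributions, odds ratios and correlations below are assumed.

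**1. The plan's own power figure (Aim 1).** Pooled proportion 0.62. Null SE = √(2 × 0.62 × 0.38 / 50) = 0.0971. Alternative SE = √((0.44 × 0.56 + 0.80 × 0.20) / 50) = 0.0902. Power = Φ((0.36 − 1.96 × 0.0971) / 0.0902) = Φ(1.88) = 97%. This agrees with the stated figure of over 90%, the only between-arm power in the document.

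**2. Satisfaction, odds ratio common to all cuts.** The odds at each cut are multiplied by the OR. For example, 40% satisfied on placebo gives odds 2 × 0.40/0.60 = 1.333, or 57% on Doxycycline. Simulated power without adjustment, 6,000 trials each:

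| Satisfied on placebo | OR | 5-category chi-square | Top-two chi-square | Rank-sum (ordinal) |
|---|---|---|---|---|
| 40% | 2 | 29.4% | 42.7% | 48.5% |
| 30% | 2 | 28.8% | 38.4% | 48.3% |
| 55% | 2 | 28.9% | 38.3% | 47.7% |
| 40% | 3 | 67.2% | 79.3% | 86.4% |
| 30% | 3 | 66.0% | 78.1% | 86.1% |
| 55% | 3 | 64.0% | 70.2% | 84.1% |

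Two further placebo distributions (25% and 40% in the top two categories) gave 29%, 35-42% and 48-49% at OR 2. So at OR 2 the ordinal test gains about 20 points over the 5-category chi-square (48.5 − 29.4 = 19.1, for example) and roughly 6 to 13 over the dichotomy. With no true effect, the 5-category test rejected in 4.5-4.9% of trials, so it is valid.

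**3. Treatment only moves women across the satisfied line.** Suppose satisfaction tracks bleeding control one-to-one, each course controls 100 − 44 = 56%, and half of those needing open-label Doxycycline receive it before week 13 (all assumed):
- placebo: 0.20 + 0.5 × 0.80 × 0.56 = 0.424;
- Doxycycline: 0.56 + 0.5 × 0.44 × 0.56 = 0.683;
- OR = (0.683/0.317) / (0.424/0.576) = 2.9.

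Hold the split within satisfied and within not satisfied fixed. Power is then 76% for the dichotomy, 64% for the rank test and 52% for the 5-category chi-square. If all are treated, the rates are 0.20 + 0.80 × 0.56 = 0.648 and 0.56 + 0.44 × 0.56 = 0.806, with power 43% (dichotomy) and 31% (rank test). The ordinal test loses about 12 points in both cases. With adjustment, the first case gives 74-77% for the dichotomy and 67-75% for the ordinal model.

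**4. Adding baseline score and factors.** OR 2, common across cuts, every test held to a true 5% size. The pairs are the two placebo distributions with 25% and 40% satisfied:

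| Latent correlation | Dichotomy, unadjusted | Dichotomy, adjusted | Ordinal, unadjusted | Ordinal, adjusted |
|---|---|---|---|---|
| 0.3 | 35.9 / 40.1% | 36.5 / 41.5% | 47.9 / 50.0% | 49.7 / 50.4% |
| 0.5 | 37.0 / 41.7% | 39.3 / 45.3% | 50.0 / 49.3% | 56.3 / 56.9% |

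The dichotomy gains 0.6, 1.4, 2.3 and 3.6 points. The ordinal model gains 1.8 and 0.4 points at correlation 0.3, and 6.3 and 7.6 at 0.5. The factors were given no effect on satisfaction here, so any prognostic value they have is not counted.

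**5. An extreme non-proportional case.** If women move only from neutral to satisfied (15/20/25/25/15% versus 15/20/5/45/15%), adjusted proportional odds has 15-17% power, the dichotomy 54-55% and the 5-category chi-square 72-74%.

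**The case against.** The strongest reply is that the plan predicts a difference in satisfaction rates, that a chi-square on proportions answers exactly that, and that section 5.4.2 already plans adjusted logistic models and confidence intervals for satisfaction. Much of this stands. It is the reason to keep a rate as the main result rather than replace it with a cumulative odds ratio. It does not rescue the 5-category reading. It also leaves the adjusted model supplementary, with no covariates named.

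A second reply is that baseline may add little. Every randomized woman enters with unacceptable bleeding, so baseline scores may bunch together. That also stands: the gain is small at correlation 0.3 and immaterial at zero.

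A reader might infer more than the documents support:
- *That the chi-square is wrong.* It holds its size.
- *That proportional odds must be the main test.* Steps 3 and 5 show that it can lose, and nothing in the plan indicates a common odds ratio.
- *That the Aim 2 item is undefined.* Section 5.3.2(C) names satisfaction with ESI, which is item (a).
- *That the 5-category chi-square is always weakest.* It trails the ordinal analysis in steps 2 and 3, but leads in step 5.

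**Conclusion.** The point holds as one of efficiency on a secondary aim. The main week-13 test leaves out the baseline score and the minimization factors. Read literally, it also treats an ordered item as unordered. Under a common odds ratio of 2, the 5-category form costs about 20 points of power against an ordinal test. It also trails both alternatives in the across-the-line case. Adjustment adds about 0-4 points to the dichotomy at correlation 0.3-0.5, at no cost in data. The choice between ordinal model and dichotomy goes either way (roughly +6 to +13, or about −12, points) and is not an error in the plan.

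Every size rests on assumed distributions, correlations and effects. At an odds ratio of 2, Aim 2 stays underpowered under all of these tests. The missing covariate list, and the missing rule for surveys completed at removal, are minor clarifications. The primary endpoint is unaffected.

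**What to change.** In section 5.4.2:

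1. Make the main week-13 analysis of satisfaction with ESI (item a) a logistic model for the top two categories versus the rest, using the cut in section 5.4.1. Include arm, that item's score at randomization, age group, postpartum status and BMI group. Report the risk difference with its 95% CI.
2. Prespecify a proportional-odds model with the same covariates as supportive, and state that the logistic model decides. If the sponsor prefers the reverse, say so in advance.
3. Do not use a 5-category chi-square for this comparison.
4. State whether a survey completed at removal before week 13 stands as the week-13 score. Using it keeps those women in the comparison.

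The cost is wording only, since every covariate is recorded by randomization. There are two drawbacks. Keeping the dichotomy as the deciding analysis gives up some power if the odds ratio really is common across cuts. The adjusted odds ratios are conditional (at correlation 0.5, a marginal 2 is estimated at about 2.25 in the proportional-odds model), which is a reason to report the risk difference. The supportive model's likelihood-ratio test also runs slightly high at this sample size (5.6-6.5%). The chi-square for the primary endpoint can stay.
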